One of the main aims of this registry-based study is to further evaluate these serious neurological events under routine medical care. Data from 2 existing networks of ALS disease registries, the TRICALS network's Precision-ALS programme [McFarlane 2023] and the ALS/NMD NHC [Berger 2023], will be leveraged for this study. In both registry networks, data collection is encounter-based with comprehensive assessments of healthcare received and health outcomes. This study will provide additional safety data to further characterize the safety profile of tofersen, both regarding the risks mentioned above and other serious events, during long-term use in routine clinical practice. As with many clinical studies, the tofersen clinical development programme employed specific exclusion criteria including female participants who were pregnant, as a result there are no clinical data from the use of tofersen in pregnant women. However, data from studies in animals in which tofersen is not pharmacologically active do not indicate direct or indirect harmful effects with respect to reproductive toxicity. This registry-based study provides an opportunity to collect frequency data on pregnancy and pregnancy outcome among people with *SOD1*-ALS and are included as a secondary study objective.

While the primary aim of this study is to evaluate long-term safety of tofersen among people with *SOD1*-ALS, [REDACTED]

[REDACTED]

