## 9.7. Data Analysis

Planned analyses are summarized below and will be described in more detail in a separate statistical analysis plan (SAP).

Data will be analyzed separately for each registry network. However, the analysis performed will be harmonized as much as possible, where data capture and actual participant and event numbers allow.

Statistical analyses will generally be descriptive in nature and there is no *a priori* hypothesis to be tested. Continuous variables will be described with summary statistics including number of observations, mean, standard deviation, median, first quartile, third quartile, and minimum and maximum values. Categorical data will be described in terms of frequencies and percentages. An additional category of 'missing' will be added to account for missing data. Event rates may also be calculated as deemed appropriate.

All efforts will be made to collect data as completely as possible but incomplete dates could occur and this must be considered when evaluating the event and censoring times. Partial dates with missing information will be imputed as detailed in the SAP.

Analyses will be conducted on all adults with *SODI*-ALS enrolled in Precision-ALS and ALS/MND NHC, including participants treated with tofersen as well as untreated participants. All analyses will be stratified by tofersen treatment status except secondary objective 2 (assessed among tofersen users only). Further details on the exclusion of data from clinical trials and the impact on index dates will be detailed in the SAP.

Comparisons between treated and untreated patients for outcomes related to safety, tolerability, or effectiveness are not planned, owing to the inability to address bias in the analyses, given the small sample size for *SODI*-ALS and uncertainties around patient selection for tofersen treatment.

All participants, including participants who discontinue tofersen, will be followed until death or loss to follow-up. Sensitivity analyses will be performed censoring data 150 days (5 half-lives) after tofersen discontinuation (after which data will then be excluded from the analysis) [Benet and Zech 1981; FDA 2003; Rowland and Tozer 2010].

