### **9.7.2. Secondary Objectives**

#### **9.7.2.1. New Comorbid Conditions, Pregnancy and Pregnancy Outcome**

Frequency of new comorbid conditions, pregnancy and pregnancy outcomes will be reported. Event rates may also be calculated if deemed appropriate.

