**Pregnancy data**

Variables	Data type / categories and responses
Date pregnancy confirmed	[date]
Data of last menstrual period	[date]
Ectopic pregnancy	Y/N
Date of outcome	[date]
Outcome	Live birth without congenital anomaly
	Live birth with congenital anomaly
	Premature birth
	Spontaneous abortion/miscarriage
	Elective termination
	Stillbirth
	Unknown

CONFIDENTIAL

The information contained herein may not be used, disclosed, or published without the written consent of Biogen MA Inc.

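### The 150-day sensitivity analysis exempts no endpoint; applied to pregnancy as written, it would keep early losses and drop later births and birth defects when tofersen is stopped early in gestation

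*Protocol*

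**What the plan says.** Two adjacent sentences in Protocol Section 9.7 settle the status of the rule. The main analysis has no cut at discontinuation: "All participants, including participants who discontinue tofersen, will be followed until death or loss to follow-up". The cut comes next, as a sensitivity analysis: "Sensitivity analyses will be performed censoring data 150 days (5 half-lives) after tofersen discontinuation", with the parenthesis "after which data will then be excluded from the analysis". It acts on data in general, and no endpoint is named or excepted. Elsewhere the protocol does tailor rules by objective: "All analyses will be stratified by tofersen treatment status except secondary objective 2", and Section 9.7.1.2 gives SAEs their own index date.

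On pregnancy, Section 9.7.2.1 says: "Frequency of new comorbid conditions, pregnancy and pregnancy outcomes will be reported". Section 7.2 gives the reason for collecting these data: "there are no clinical data from the use of tofersen in pregnant women". Annex 3 makes congenital anomaly one of the SAE criteria. Annex 4 lists the possible pregnancy outcomes, among them miscarriage, termination, premature birth, and live birth with or without an anomaly. It also collects the date of each infusion, the discontinuation date, the pregnancy outcome date and the last menstrual period (LMP), entered as "Data of last menstrual period".

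Section 9.7 leaves further detail to the SAP. In Annex 2, the comment on item 10.8 does the same for sensitivity analyses, and the comment on items 5.2, 5.3 and 5.5 does so for exposure data capture. The SAP is not at hand.

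**The concern.** A window of five half-lives suits an event that depends on drug being present when the event occurs. Pregnancy outcome works differently. What matters is whether drug was present around conception or during gestation, while the outcome is recorded at the end of pregnancy, possibly months after the last infusion. A cut at a fixed time after discontinuation therefore selects on the length of the pregnancy. Losses tend to fall before the cut and births after it.

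The pregnancy itself would usually still be counted, because it is confirmed before the cut. Only its outcome would drop out, and which outcomes drop out depends on what they are. A sensitivity analysis meant to focus on exposed time would then show a distorted outcome distribution for exactly the pregnancies of interest, in a study that presents pregnancy outcome as a gap it can help to fill.

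**Working it through.** **Inputs from the protocol.** The cut is 150 days after discontinuation, described as 5 half-lives (Section 9.7). This implies 150/5 = 30 days per half-life. The protocol gives no half-life, so the 150 days cannot be checked independently; they are taken as stated. In weeks, 150/7 = 21.4.

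**Assumptions not in the protocol.** Term is 40 weeks (280 days) from LMP, with births at 37 to 42 weeks shown as a range. A birth defect is dated at birth or later. The stop is the recorded discontinuation date.

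**Cut-off.** A birth at *T* weeks is dropped if it comes more than 150 days after the stop, that is, if tofersen stopped before gestational day 7*T* − 150.

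| Birth at (weeks) | 7*T* − 150 (days) | In weeks |
|---|---|---|
| 37 | 259 − 150 = 109 | 15.6 |
| 39 | 273 − 150 = 123 | 17.6 |
| 40 | 280 − 150 = 130 | 18.6 |
| 42 | 294 − 150 = 144 | 20.6 |

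**What happens at given stopping times** (birth at day 280):

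| Stop (weeks) | Stop (day) | Cut (day) | Cut (weeks) | Stop to birth (days) | Birth in sensitivity analysis |
|---|---|---|---|---|---|
| 6 | 42 | 192 | 27.4 | 238 | dropped |
| 12 | 84 | 234 | 33.4 | 196 | dropped |
| 16 | 112 | 262 | 37.4 | 168 | dropped |
| 20 | 140 | 290 | 41.4 | 140 | kept |

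**The contrast.** A loss at week 10 after a stop at week 6 occurs 70 − 42 = 28 days after the stop and is kept. A 40-week birth after the same stop occurs at 238 days and is dropped. After a stop at week 12, the only live births that can remain are those before 33.4 weeks.

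**Main analysis.** With no cut at discontinuation, none of these outcomes is removed.

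**The case against.** The strongest reply is that this is a supplementary analysis and that its endpoint scope belongs in the SAP. The protocol never says outright that the cut applies to pregnancy; that follows only from the unrestricted wording. With outcomes reported as counts, the uncensored and censored results would be visible together. Section 9.9 also promises a case-level review of SAEs that looks at their timing relative to dosing. That review would cover congenital anomalies, since they meet an SAE criterion and the SAE form prompts the pregnancy form.

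Much of this stands, and it rules out two stronger readings that a reader might infer. One is that births or birth defects disappear from the study. They do not: the main analysis keeps everyone in follow-up after discontinuation. The other is that the main analysis is itself faulty because it counts every pregnancy of a treated participant, including one conceived long after the last infusion. Secondary objective 1 is descriptive and concerns people with *SOD1*-ALS by treatment status, so that count matches the objective. Nor is the lack of an exposed-pregnancy definition an error in itself, since exposure details are deferred to the SAP.

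The reply does not dispose of the rule. The cut is stated in the protocol, without limit, in a section that elsewhere makes exceptions by objective. The case-level review does not expressly cover pregnancy outcomes that are not SAEs.

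**Conclusion.** The point holds as a flaw in how one sensitivity analysis is specified. If the 150-day cut is applied as written to pregnancy outcome or to congenital-anomaly SAEs, it excludes a term birth, or a defect dated at birth, when tofersen stopped before about 18.6 weeks' gestation (15.6 to 20.6 weeks for births at 37 to 42 weeks), and it keeps early losses. The direction is clear: that result tilts towards losses and cannot show defects found at a term birth after an early stop.

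The size in practice is conditional. It needs a pregnancy, a stop before the cut-off and a birth more than 150 days later. The protocol gives no expected number of pregnancies, so no expected count of affected outcomes can be stated. The conclusion rests on the assumed length of term and on reading the rule as covering all endpoints, which the SAP may narrow. Priority is low to moderate.

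**What to change.** State in Sections 9.7 and 9.7.2.1 that the 150-day censoring does not apply to pregnancy outcome or to congenital-anomaly SAEs.

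For the exposure-limited analysis, replace it with a rule tied to the pregnancy: *A pregnancy counts as tofersen-exposed if any infusion falls between 150 days before LMP and the end of the pregnancy. Its outcome is counted whenever it occurs.* The 150 days reuse the protocol's own five half-lives; the window itself is new to the plan.

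Keep the main analysis of all pregnancies by treatment status. Within treated participants, show exposed and non-exposed pregnancies separately as an added descriptive split.

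The cost is one or two sentences, matching text in the SAP, and a little extra programming. No new data are needed, because LMP, outcome and infusion dates are already in Annex 4.

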## 6. MILESTONES

**Table 2: Milestones for Protocol 233AS401**

Milestone	Planned Date
Start of data collection (data extraction) a	30 January 2026
End of data collection (data extraction) a, b	30 July 2033
Interim progress reports	Annually (with reassessment)
Registration in HMA-EMA catalogue of real-world data studies c	31 October 2025
Report of study results	Within 12 months of end of data collection (data extraction)

a Per European Union (EU) Guideline on good pharmacovigilance practices ([[EMA \(EMA/330405/2012\) 2012](#)] Section A.1), the start and end of data collection for secondary use of data are the date from which data extraction starts and the date from which the analytical datasets are available.

b The end of data extraction for this study is set to 7 years from start of data extraction. The expected end date of data extraction may be modified based on study progress, which will be reviewed annually as part of the reassessment procedure. The potential continuation of the study will be determined based on the results obtained at the targeted end of data collection (data extraction).

c Study will be registered in Heads of Medicine Agency-European Medicines Agency (HMA-EMA) catalogue of real-world data studies following Pharmacovigilance Risk Assessment Committee approval of final protocol and prior to study initiation.

CONFIDENTIAL

The information contained herein may not be used, disclosed, or published without the written consent of Biogen MA Inc.

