### 7.2. Study Rationale and Regulatory Background

This study is part of the planned pharmacovigilance activities for tofersen (tradename: Qalsody™). Qalsody has been approved in multiple regions, including by both the United States Food and Drug Administration (US FDA) (April 2023) and the EMA (May 2024). In Europe, Qalsody was granted marketing authorisation (MA) under exceptional circumstances with the indication of treatment of adults with ALS associated with a mutation in the *SOD1* gene. As part of the conditions of the MA under exceptional circumstances, the marketing authorisation holder (MAH) agreed to conduct and submit the results of this observational registry-based study (Study 233AS401), to further evaluate the long-term safety of tofersen in people living with *SOD1*-ALS. This specific obligation is included as a Category 2 study in the EU risk management plan (RMP).

The safety and efficacy of tofersen was assessed in clinical trials and has a positive benefit/risk profile in the treatment of adults with *SOD1*-ALS. However, information on long-term use is limited. Given this and the rarity of the indication, this non-interventional registry-based study is being conducted as part of the post approval pharmacovigilance activities to further evaluate the long-term safety of tofersen among people with *SOD1*-ALS under routine medical care.

The safety profile is based on 166 participants with ALS (162 with *SOD1*-ALS) that were exposed to any dose of tofersen in the clinical development programs. Of these, a total of

CONFIDENTIAL

The information contained herein may not be used, disclosed, or published without the written consent of Biogen MA Inc.

147 people with *SOD1*-ALS received tofersen 100 mg, for 368.83 participant-years. The median exposure for this group was 148.4 weeks. Most adverse events (AE) reported during treatment with tofersen were consistent with the types and severities of AEs seen in people with *SOD1*-ALS or events observed in the context of the lumbar puncture (LP) procedure.

In the clinical studies, serious neurological events of myelitis, radiculitis, increased intracranial pressure, papilloedema, and aseptic meningitis have been reported in participants receiving tofersen and not in placebo treated participants. Details on these serious reactions are included in the EU product information.

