#### 9.4. Data Sources

Disease registries have been previously used to assess the long-term safety in post marketing commitments requested by the US FDA and the EMA. This study focuses on the secondary use of data from 2 large networks of ALS disease registries, the TRICALS network's Precision-ALS programme [McFarlane 2023] and ALS/MND NHC [Berger 2023]. These data sources are networks of ongoing longitudinal ALS disease registries. Individual participant-level data will be collected at routine clinic visits by each registry network (Section 9.3). In advance of initiation of this study, both networks have been engaged to implement treatment and SAE data collection in their registries. The Precision-ALS data platform was developed by a consortium comprising international clinicians from the European ALS Research entity TRICALS working closely with computational data and scientists based in the Science Foundation Ireland-funded ADAPT research centre in Ireland [ADAPT 2024]. TRICALS is the world's largest network of specialty ALS centres, collecting and combining participant data from centres in multiple countries across Europe. The Precision-ALS programme is a research platform, consisting of a longitudinal data collection infrastructure based on electronic medical records as well as primary data collection for some variables. Precision-ALS includes ALS referral centres across multiple European countries. Precision-ALS has collated data from 21,000 people living with ALS from 9 participating sites [McFarlane 2023; Precision ALS 2024]. As the Precision-ALS platform expands, additional countries may be considered for inclusion in the platform and study. ALS/NMD NHC is an established multidisciplinary clinic-based registry network that prospectively and longitudinally captures important clinical information about the disease process from people living with ALS. The ALS/NMD NHC consists of academic medical centres in the United States and Europe. However, to avoid potential duplication of data from national registries already included in the Precision-ALS programme, only data from centres in the United States will be included. Over 2100 people living with ALS have enrolled in this natural history study. Data collection, curation, and analysis is through NeuroBANK, a flagship clinical research platform which is run by the Neurological Clinical Research Institute at Massachusetts General Hospital [Berger 2023; data4cures 2024].

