Data collected while a person with *SODI*-ALS is participating in an interventional clinical trial (with tofersen or any other investigational medicinal product) will be excluded since this study will focus on real-world data and the results from interventional clinical trials will be available elsewhere.

CONFIDENTIAL

The information contained herein may not be used, disclosed, or published without the written consent of Biogen MA Inc.

The analysis population and definition of index date for statistical analysis will differ by treatment status and by study objective. In general terms, index date will be the date of tofersen treatment for data from participants in the treated group or date of enrolment into the registry for data from participants in the untreated group [REDACTED]

[REDACTED] Sensitivity analyses will be performed excluding retrospectively treated participants (i.e., those who initiated tofersen treatment prior to enrolment in the registry networks).

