#### **9.7.1.2. SAEs**

Frequency of all reported SAEs will be summarized and presented by Medical Dictionary for Regulatory Activities (MedDRA) system organ class (SOC)/preferred term (PT) or International Classification of Diseases (ICD), as appropriate. Event rates may also be calculated if deemed appropriate.

The analysis of SAEs will be based on data collected only after implementation of SAE reporting forms and thereby the index date will be defined as the latter of tofersen initiation, registry enrolment, or implementation of SAE forms as appropriate, and the analysis population will consist of participants who are still alive at SAE form implementation.

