This study will include data from both prevalent and incident tofersen users. The assessment of incident drug users is a key study design feature to avoid immortal time bias [Suissa 2008] and depletion of susceptibles in real-world evidence studies [Moride and Abenheim 1994]. However, in the case of ultra rare diseases like *SODI*-ALS, the inclusion of participants with prevalent *SODI*-ALS, including tofersen users at the start of data extraction, will allow the collection of as much data as possible. The potential biases resulting from inclusion of prevalent users is acknowledged, and the analysis will take these potential biases into consideration (e.g., reporting results separately for prevalent and incident tofersen users if deemed appropriate). The safety profile of tofersen will be characterized through a review of the SAE data reported from individual participants during the study with a particular focus on the relationship assessment recorded on the SAE forms, temporal relationship of SAEs to tofersen dosing, the

CONFIDENTIAL

The information contained herein may not be used, disclosed, or published without the written consent of Biogen MA Inc.

consistency of SAE reports with tofersen clinical trial data and published literature, biologic plausibility, and confounding factors including known comorbidities of ALS.

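### For SAEs, the sensitivity analysis that drops people treated before enrolment keeps those who enrolled, then started tofersen, before the SAE forms went live

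*Protocol*

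**What the plan says.** Section 9.7 says that index dates and analysis populations differ by treatment status and by objective. It then commits to a sensitivity analysis that leaves out retrospectively treated participants and defines them as "those who initiated tofersen treatment prior to enrolment in the registry networks". The only anchor in that definition is enrolment.

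Section 9.7.1.2 sets different rules for SAEs. On the data used: "The analysis of SAEs will be based on data collected only after implementation of SAE reporting forms". On the start of follow-up: "the index date will be defined as the latter of tofersen initiation, registry enrolment, or implementation of SAE forms as appropriate". On who is included: "the analysis population will consist of participants who are still alive at SAE form implementation".

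Section 9.4 shows that the SAE forms were added to registries already running: "both networks have been engaged to implement treatment and SAE data collection in their registries". Section 9.9 gives the reason for caring about new users: "The assessment of incident drug users is a key study design feature to avoid immortal time bias". Sections 9.1 and 9.9 also name depletion of susceptibles. Section 9.9 mentions separate reporting of prevalent and incident users, but only as an example to be used at discretion, and it does not define the two groups relative to the SAE index date.

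**The concern.** The exclusion and the SAE index date use different clocks. A participant may have been in the registry for years, started tofersen after enrolment, and had several doses before the SAE forms existed at their site. Enrolment preceded treatment, so the rule keeps this person. For the SAE endpoint they are nonetheless a prevalent user: events during the first doses fall outside the data, and the person enters only by being alive at form implementation.

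SAE frequency is a primary endpoint, and further evaluation of the serious neurological events is one of the study's main aims. If these events cluster early in treatment, both the main and the sensitivity results would contain people whose early period is missing. Agreement between the two would then say less about prevalent-user bias than it appears to.

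**Working it through.** **Inputs.** Let T be tofersen start, E registry enrolment and F SAE-form implementation at the participant's site.

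- Exclusion rule (Section 9.7): drop if T < E.
- SAE index date (Section 9.7.1.2): max(T, E, F), with survival to F required.
- Early exposure is unobserved for SAEs when T < max(E, F).

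**All six orderings.**

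| Ordering | SAE follow-up starts at | Early exposure unobserved? | Dropped by the rule? |
|---|---|---|---|
| T < E < F | F | yes | yes |
| T < F < E | E | yes | yes |
| F < T < E | E | yes | yes |
| **E < T < F** | **F** | **yes** | **no** |
| E < F < T | T | no | no |
| F < E < T | T | no | no |

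Four orderings leave early exposure unobserved. The rule removes three and keeps E < T < F. Because SAE follow-up starts at F, the time from T to F is not counted in the denominator. What remains is selection of people who tolerated and survived the early period.

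**Can the group exist?** Approval was in April 2023 (US) and May 2024 (EU), and extraction starts on "30 January 2026". If the forms went live near that date (an assumption), the window for E < T < F would be about 2.75 years in the US (end of April 2023 to 30 January 2026) and 1.67 years in the EU (end of May 2024 to the same date). Earlier forms shorten it. The group is empty only if the forms preceded every post-enrolment start at every site.

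**The plan's own figures.** These reproduce and are not in dispute:

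- Rate: 12 / 368.83 = 0.0325, stated as 0.033 per person-year.
- Treated follow-up: 25 × 5 × 0.40 × 2 = 100 person-years.
- Exact Poisson 95% limits for 4 events in 100 person-years: 0.0109 to 0.1024, as in Table 3.

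**Illustration only.** None of these settings is in the protocol. Suppose the first 6 months on drug carry k times the later hazard h, the average over 2.5 years is 0.033, everyone has 2 years of follow-up, and a share f of the sensitivity set is E < T < F with those 6 months unobserved. Then

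h = 0.033 × 2.5 / (0.5k + 2)

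rate = [(1 − f)(0.5kh + 1.5h) + f × 2h] / 2

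| k | f = 0 | f = 10% | f = 20% | f = 40% |
|---|---|---|---|---|
| 1 | 0.0330 | 0.0330 | 0.0330 | 0.0330 |
| 2 | 0.0344 | 0.0337 | 0.0330 | 0.0316 |
| 4 | 0.0361 | 0.0345 | 0.0330 | 0.0299 |

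For k = 4, h = 0.0825 / 4 = 0.0206. Relative to f = 0, the rate falls by about 4%, 9% and 17%. For k = 2 it falls by about 2%, 4% and 8%. For k = 1 it does not change.

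**The case against.** The strongest reply is that the protocol never says this sensitivity analysis is meant to isolate incident users for SAEs. The sentence follows the general index-date rule, for which treatment before enrolment is a coherent cut, and redacted text stands just before it. Section 9.9 acknowledges prevalent-user bias and offers separate reporting. Since Sections 9.1 and 9.9 count tofersen users at the start of extraction among the prevalent cases, many of the people at issue could be separated there. The study is descriptive, SAE rates are optional, safety is also judged by review of individual cases, and the shifts illustrated are small beside an interval of 0.0109 to 0.1024.

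Much of this stands, and it limits the weight of the point. It does not close the gap. The definition is complete and legible, and it uses one anchor for every objective in a section that says index dates differ by objective. The separate reporting is discretionary, so this exclusion is the only committed analysis that addresses prevalent use.

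A reader might go further in three ways that the protocol does not support:

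- **Trial exposure.** One might infer the same fault for people who enrolled, received tofersen in a trial and then moved to commercial drug. Section 9.7 leaves the exclusion of trial data and its effect on index dates to the SAP, so this is not part of the point.
- **A large bias.** Assuming that the first year is 40% of exposure, that its rate is 2 to 5 times the later rate, and that 20–60% of person-years come from affected people gives an understatement of 6–37%. None of these inputs is documented, and the calculation treats every affected person as already past the first year when the forms arrive.
- **Lost deaths.** Vital status is collected and there is a mortality form. Deaths before the forms fall outside the SAE analysis population; they are not necessarily lost to the registry.

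**Conclusion.** The point holds as a mismatch between two stated rules. For the SAE objective, the exclusion in Section 9.7 leaves in participants with E < T < F, so it does not fully remove the depletion of susceptibles and survivor selection that the protocol itself acknowledges. This conclusion rests on the written definitions and on no assumed number.

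The size of the effect is unknown. It depends on the form dates, on how many people enrolled and then started tofersen before the forms, and on whether the hazard changes with time on drug; the protocol gives none of these. With a constant hazard the effect is nil. In a descriptive study of this precision, this is an inexpensive correction worth making, not a flaw that undermines the study.

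**What to change.** In Section 9.7 or 9.7.1.2, add one sentence: for the SAE objective, the sensitivity analysis excludes participants whose recorded tofersen start date precedes the SAE index date, that is, the later of enrolment and SAE-form implementation at their site. Use the same split for any separate prevalent and incident reporting of SAEs under Section 9.9. This removes all four orderings with unobserved early exposure.

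The treatment start date is already in the tofersen treatment log (Annex 4), and the form-implementation date is already needed for the SAE index date. The cost is fewer person-years in this one sensitivity analysis, by an amount that cannot be stated until the form dates are known. The main analysis is unchanged.
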